11.6.4. Vital Sign Analyses

Descriptive statistics will be provided for the vital signs measurements and changes from baseline by scheduled time of evaluation and using the Safety Evaluation Set, as well as for the change from baseline. The baseline value is defined as the last non-missing value before the initial administration of study treatment.

11.6.5. Physical Examination Analyses

A listing of physical examination findings will be provided for the Safety Analysis Set.

11.6.6. Interstitial Lung Disease Analysis and Adjudication

An external ILD AC will be established for this study. Details on the membership, responsibilities, and working procedures of the external ILD AC will be described in its

own charter, provided as a separate document in the study file. To ensure adequate and relevant independent evaluation, systematic additional data collection will be conducted for all cases that will be brought for ILD adjudication, these additional data collections will cover a more in-depth medical history (eg smoking, radiation, COPD and other chronic lung conditions, etc), diagnostic evaluation, treatment and outcome of the event. The data collection will be triggered for any safety event reported using a Medical Dictionary for Regulatory Activities (MedDRA) PT from the current ILD standardized MedDRA query (SMQ)

The ILD AC will adjudicate ILD cases (including potential ILD) on an ongoing basis. Adjudication of ILD cases will be based on evaluation of eCRFs and source documents including but not limited to chest high-resolution CT, arterial blood gases, and diffusing capacity of lung carbon monoxide (DLCO). The ILD AC will review ongoing cases of ILD to make the final determination of ILD diagnoses to guide Sponsor decisions regarding trial suspension or trial discontinuation and to provide assessment of ILD prevalence at the end of study. Findings of the ILD AC with its recommendations will be provided to the Sponsor.

11.7. Interim Analyses

No formal interim analysis is planned, except for the assessment of the RDE.

11.8. Data Monitoring Committee

[figure not shown]
Not applicable.

11.9. Sample Size Determination

Phase 1 dose escalation : ≥ 18 subjects

The Dose Escalation part of this study consists of mCRM with EWOC design with at least 3 DLT-evaluable subjects per dose level. At least 18 DLT-evaluable subjects are needed to reach an accurate estimate of the maximum tolerated dose (MTD). There will be at least 18 DLT-evaluable subjects treated to reach an accurate estimate of the RDE in Dose Escalation, with at least 6 subjects treated at the final selected dose.

CCI

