^b Administer with a meal, with 240 mL of water. On the morning of Endpoint ECG days, breakfast should be started 30 minutes prior to dosing and should be completed within approximately 20 minutes. For all other dosings, it is recommended that meals (breakfast or dinner) be completed within approximately 30 minutes, and DS-1205c should be taken immediately after meal completion. Doses of DS-1205c should be taken approximately 12 hours apart.

^c Co-administer with morning dose of DS-1205c.

Dose escalation will be guided by the modified Continuous Reassessment Method (mCRM) using a Bayesian logistic regression model (BLRM) following the escalation with overdose control (EWOC) principle. In this method, a decision to escalate to the next cohort is based on review of all subjects who have completed the dose-limiting toxicity (DLT)-evaluation period.

The DLT-evaluation period is defined as the 7 days of Cycle 0 plus the 21 days of Cycle 1 (28 days total). A DLT-evaluable subject is defined as a subject who has received DS-1205c and EITHER has completed minimum safety evaluation requirements over the DLT-evaluation period OR has experienced a DLT during the DLT-evaluation period.

The RDE will be decided based on an overall assessment of available safety and tolerability data from Cycle 1 and beyond, and all available PK, biomarker, and tumor response data. Dose Escalation will be stopped if any of the following occur: (a) at least 6 evaluable subjects have been enrolled at the RDE with at least 18 evaluable subjects in total enrolled in Dose Escalation, or (b) at least 9 evaluable subjects have been enrolled at a particular dose level, the model recommends continuing at the same dose level, and the posterior probability of the DLT rate falling within the target DLT interval is $\geq 50\%$, or (c) the starting dose is too toxic.

Study Duration:

Dose Escalation

- Enrollment is planned to occur over approximately 12 months.
- Treatment and follow-up will be completed when all subjects have either discontinued study treatment or completed last study visit

The number of treatment cycles is not fixed in this study. Subjects will continue study treatment until withdrawal of consent, progressive disease (PD), or unacceptable toxicity for all subjects in Dose Escalation and Dose Expansion.

Study Sites and Locations: Approximately 20 clinical sites within Japan. Additional sites and countries may be added as needed.

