3.2.1.5. Stopping Rule for Recommended Dose for Expansion Determination

Dose Escalation will be stopped if any of the following occur:

- a. at least 6 evaluable subjects have been enrolled at the RDE level with at least 18 evaluable subjects, in total, enrolled in Dose Escalation, OR
- b. at least 9 evaluable subjects have been enrolled at a particular dose level, the model recommends continuing at the same dose level, and the posterior probability of the DLT rate falling within the target DLT interval is $\geq 50\%$.
The target DLT interval is defined as $16\% < \text{DLT rate} \leq 33\%$
(Section 11.11.3), OR
- c. the initial dose level is too toxic.

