11.11.3. Escalation With Overdose Control Principle

Dose recommendation for the next cohort of patients will be based on summaries of the posterior probability of DLT rate for provisional doses.⁴⁴ After each cohort of subjects completes DLT evaluation during Cycle 1, the joint posterior distribution of the BLRM parameters will be generated according to the Bayes' theorem based on the likelihood function of the accumulated DLT data from Cycle 1 and the prior distribution. Posterior probabilities of DLT rate at different dose levels will then be obtained from updated BLRM, and summarized for DLT rate in 4 different ranges: under-dosing (ie, DLT rate within [0, 0.16]), target toxicity (ie, DLT rate within [0.16, 0.33]), excessive toxicity (ie, DLT rate within [0.33, 0.60]), and unacceptable toxicity (ie, DLT rate within [0.60, 1.00]). The dose level recommended by mCRM for dosing next cohort will be based on these probabilities according to the EWOC principle. The EWOC principle requires that the mCRM recommended dose for the next cohort of subjects is the one with the highest posterior probability of the DLT rate in the target DLT rate range of [0.16, 0.33] among all doses fulfilling the overdose control constraint that there is less than 0.25 of probability for DLT rate > 0.33 (probability for excessive or unacceptable toxicity).

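### Section 11.9 promises at least 18 DLT-evaluable subjects without condition, but stopping rule (b) can end Dose Escalation and lead to an RDE with 15

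*Combined protocol and SAP*

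**What the plan says.** Section 11.9 gives the size of Dose Escalation three times, each time without a condition:

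- Opening line: "Phase 1 dose escalation : ≥ 18 subjects".
- For the MTD: "At least 18 DLT-evaluable subjects are needed to reach an accurate estimate of the maximum tolerated dose (MTD").
- For the RDE: "There will be at least 18 DLT-evaluable subjects treated to reach an accurate estimate of the RDE in Dose Escalation". It adds that no fewer than 6 of them are to be at the dose finally selected.

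Section 3.2.1.5 opens with "Dose Escalation will be stopped if any of the following occur" and joins three rules by OR. The synopsis repeats them.

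- Rule (a) reads: "at least 6 evaluable subjects have been enrolled at the RDE level with at least 18 evaluable subjects". The 18 is the overall count across doses.
- Rule (b) begins: "at least 9 evaluable subjects have been enrolled at a particular dose level, the model recommends continuing at the same dose level". It further requires at least 50% posterior probability for the target interval (DLT rate above 16% and up to 33%). No total is given.
- Rule (c): the initial dose is too toxic.

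Section 3.2.1.6 has the RDE determined once the stopping criteria are met, whichever rule applied. The synopsis, under planned sample size, speaks of approximately 18 subjects.

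**The concern.** Section 11.9 presents 18 as both necessary and guaranteed. The stopping rules make it neither, because rule (b) can act before 18 subjects have been evaluated and an RDE then follows. Rule (c) is not part of the point: it can also stop the trial early, but it yields no RDE.

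Determining the RDE is part of the primary objective (section 2.1.1), and section 11.9 is the visible justification of the size for it. If rule (b) is met at 15, the sponsor must either name an RDE from fewer subjects than 11.9 says are needed, or enrol three more after a rule that says escalation stops. The document does not say whether 18 is a floor for naming an RDE or only the size reached when rule (b) does not act first.

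**Working it through.** **The stated figure.** The 18 has no error rate, precision target or operating characteristics behind it, so there is no formula to reproduce. The pair of 18 in total and 6 at the selected dose is the pair in rule (a). The question is whether rule (b) can be met with fewer than 18 under the protocol's own model.

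**Inputs.**

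- Model (11.11.1): logit π(d) = log α + β log(d/800).
- Prior (11.11.2): (log α, log β) bivariate normal with means (−1.1493, −0.5514), SDs (2.0739, 1.5228) and correlation −0.1943.
- Doses (Table 3.1): 200, 400, 600 and 800 mg BID, starting at 200 mg.
- Recommendation (11.11.3): the dose with the highest posterior probability of the target interval "among all doses fulfilling the overdose control constraint that there is less than 0.25 of probability for DLT rate > 0.33".
- Cohorts: at least 3 evaluable subjects; taken here as exactly 3.

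**Check of the prior.** At 800 mg the median DLT rate is exp(−1.1493)/(1 + exp(−1.1493)) = 0.317/1.317 = 24.1%, against a stated value of about 24.5%. At 200 mg it is 8.0% by numerical integration, against about 8%.

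**Posterior.** Proportional to the prior times the product over doses of π(d)^y (1 − π(d))^(n−y), integrated on a grid.

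**Path 1, one dose step at a time.** After 0/3 at 200 mg and 0/3 at 400 mg:

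| Data at 600 mg | Total N | P(target) at 600 | P(>0.33) at 600 | P(>0.33) at 800 | Recommended |
|---|---|---|---|---|---|
| 1/3 | 9 | 0.32 | 0.11 | 0.26 | 600 |
| 2/6 | 12 | 0.45 | 0.16 | 0.36 | 600 |
| 3/9 | 15 | 0.53 | 0.20 | 0.43 | 600 |

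In the last row there are 9 subjects at 600 mg, the model stays at 600 mg, and P(target) is at least 0.50. Rule (b) is met at 3 + 3 + 9 = 15.

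**Path 2, the recommendation followed with no step limit.** After 0/3 at 200 mg the model recommends 800 mg, where P(>0.33) = 0.21:

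| Data at 800 mg | Total N | P(target) at 800 | P(>0.33) at 800 |
|---|---|---|---|
| 0/3 | 6 | 0.15 | 0.04 |
| 1/6 | 9 | 0.32 | 0.10 |
| 2/9 | 12 | 0.45 | 0.14 |
| 3/12 | 15 | 0.54 | 0.17 |

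800 mg stays the recommended dose throughout, and rule (b) is met at 3 + 12 = 15. An importance-sampling check with 4 million draws gave 0.529 and 0.198 for the end of path 1, and 0.539 and 0.173 for the end of path 2.

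**How often.** All outcomes were enumerated in cohorts of 3. Rule (c) was read as no admissible dose and applied after the first cohort, because at 200 mg P(>0.33) is already 0.256 before any data. Rule (b) stops were counted separately from rule (c) stops. The true DLT curves are assumptions; the documents give none.

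| True DLT rate at 200/400/600/800 mg (%) | Rule (b) stop below 18, stepwise | No step limit |
|---|---|---|
| 8/14/20/24.5 (about the prior medians) | 3.9% | 9.9% |
| 5/12/24/40 | 5.6% | 8.1% |
| 8/22/40/55 | 7.1% | 1.6% |
| 2/4/7/12 | 0.5% | 5.6% |
| 22/40/55/65 | 2.5% | 0.2% |

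Every one of these stops came at 15. Among trials that reach an RDE the shares are higher. For the first curve, rule (c) as read here ends 27.8% of trials stepwise and 24.1% with no step limit, so 3.9/(100 − 27.8) = 5.4% and 9.9/(100 − 24.1) = 13.0%.

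**The case against.** The strongest reply is that early stopping is normal in a model-guided escalation and that the operating rule is clear: 3.2.1.5 and the synopsis agree, the rules are joined by OR, and 18 appears only in (a). Section 11.9 then reads as an incomplete paraphrase of rule (a) rather than a competing rule. The synopsis is softer (approximately 18), and section 3.2.1.2 lets any cohort be expanded. The shortfall found is three subjects, in a minority of trials, in a descriptive Phase 1 study with no power claim.

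Part of this stands. Rule (b) itself is not at fault. The number 15 is an example, not a proven floor: it follows from cohorts of exactly 3. A coarse search that ignored the order of enrolment found data sets of 12 to 14 subjects that also satisfy rule (b). Path 1 needs a limit of one dose step that the protocol does not state, and path 2 needs the sponsor to follow a direct move from 200 to 800 mg. The shares rest on assumed curves, and those among trials reaching an RDE also depend heavily on how rule (c) is read.

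None of it makes 11.9 conditional. A paraphrase that omits rule (b) still says that 18 are needed and will be treated. Softer wording in the synopsis does not qualify that, and permission to expand a cohort does not require enrolment up to 18.

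**Conclusion.** The point holds: section 11.9 is wrong as written. It guarantees a size that 3.2.1.5 does not, and it calls necessary for accuracy a number that rule (b) treats as dispensable. The protocol's own model, prior and overdose limit allow an RDE after 15 DLT-evaluable subjects, three fewer than stated.

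Over the five assumed curves the chance of a rule (b) stop below 18 is 0.5% to 7.1% stepwise and 0.2% to 9.9% with no step limit. These figures assume cohorts of 3 and strict use of the model recommendation. Backfilling, cohort expansion, intermediate doses and sponsor judgement were not modelled. The textual contradiction needs none of these assumptions. It should be corrected, but it does not call the design into question.

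**What to change.** Reconcile 11.9 with 3.2.1.5. Restate the size as at least 18 DLT-evaluable subjects unless Dose Escalation stops earlier under 3.2.1.5 (b) or (c), and carry that condition to the opening line and to the RDE sentence. Remove the sentence that at least 18 are needed for an accurate MTD estimate, or make it conditional in the same way.

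This changes wording in 11.9 only; no dose, stopping rule or design feature is altered. The cost is that the stated size looks slightly less favourable. If the sponsor in fact intends 18 as a floor for naming an RDE, 3.2.1.5 does not say so. That would be a design decision for the sponsor, not a correction of wording.

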3.2.1.2. Cycle 1 and Beyond (Combination Therapy)

In Cycle 1 and beyond, DS-1205c will be taken BID in combination with 250 mg QD of gefitinib in 21-day cycles, as outlined in detail in the Schedule of Events, Dose Escalation, (Cycle 1 and Beyond) ([Table 6.2](#)).

Dose escalation of DS-1205c to determine the RDE will be guided by the modified Continuous Reassessment Method (mCRM) using a Bayesian logistic regression model (BLRM) following the escalation with overdose control (EWOC) principle (Section [11.11](#)). The logistic regression model for the dose-response (DLT rate) relationships will include 2 parameters: the intercept and slope. The DLT-evaluation period is defined as the 7 days of Cycle 0 plus the 21 days of Cycle 1 (28 days total). A DLT-evaluable subject is defined as a subject who has received DS-1205c and either has completed minimum safety evaluation requirements over the DLT-evaluation period or has experienced a DLT during the DLT-evaluation period. After at least 3 DLT-evaluable subjects of each cohort complete DLT evaluation, posterior distributions of DLT rate will be derived for all dose levels based on the BLM using DLT outcome data from all assessed doses and a pre-specified prior distribution for the model parameters. The EWOC principle requires that the mCRM-recommended dose for the next cohort of subjects is the one with the highest posterior probability of the DLT rate in the target DLT rate interval with the overdose control constraint for excessive or unacceptable toxicity.

As an exception, the model will be reevaluated before enrollment of any additional subjects to the cohort if 2 DLT-evaluable subjects in the cohort experience DLT before the enrollment of the third subject. Enrollment of subjects to a new higher-dose cohort requires completion of DLT evaluation of at least 3 subjects treated in the current cohort. Subjects who have neither completed DLT evaluation nor experienced DLT will not be included in a BLM update. In the event when subjects in the previous cohort experience DLTs after enrollment of subjects to a new cohort has begun, dose level assignment of the next subject in the new cohort will be based on an updated BLM using DLT outcome data from all assessed doses. Subjects already receiving treatment will continue treatment at their assigned dose level or per dosing modification guidelines outlined in Section [5.4](#).

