11.11.2. Prior Specification for Bayesian Logistic Regression Model Parameters

The Bayesian approach requires the specification of a prior distribution for the BLRM parameters. A minimally-informative bivariate normal prior for the model parameters $(\log(\alpha), \log(\beta))$ is obtained as follows:

- The best guess of the MTD is projected to be around 800 mg in humans. The median prior probabilities of DLT are set to be approximately 8% and 24.5% at 200 mg (projected starting dose for dose escalation using mCRM) and the projected MTD of 800 mg, respectively.
- For the remaining doses, the prior medians of probability of DLT are assumed linear in log-dose on the logit-scale.
- Based on the above medians for the probability of DLT at each dose and wide prior credible intervals (obtained from minimally informative Beta distributions), the optimal parameters of the bivariate normal distribution can be obtained as follows:

Parameters	Means	Standard Deviations	Correlation
$\log(\alpha), \log(\beta)$	(-1.1493, -0.5514)	(2.0739, 1.5228)	-0.1943

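### Section 11.9 promises at least 18 DLT-evaluable subjects, but two of the three stopping rules in 3.2.1.5 have no minimum total, so escalation can end with fewer

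*Combined protocol and SAP*

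**What the plan says.** Section 11.9 (Sample Size Determination) heads Dose Escalation with a size of 18 or more. It says 18 DLT-evaluable subjects are needed for an accurate estimate of the MTD, and then gives the assurance: "There will be at least 18 DLT-evaluable subjects treated to reach an accurate estimate of the RDE in Dose Escalation". At least 6 of them are to be at the final dose. No condition is attached. Text after this paragraph is blacked out, so statements here about what is absent refer to the public text.

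Section 3.2.1.5 stops Dose Escalation if any of three rules is met:

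- (a) at least 6 evaluable subjects at the RDE and at least 18 in total;
- (b) "at least 9 evaluable subjects have been enrolled at a particular dose level, the model recommends continuing at the same dose level", with a posterior probability of at least 50% that the DLT rate lies in the target interval (16% to 33%);
- (c) "the initial dose level is too toxic".

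The synopsis repeats the three rules and gives the planned size as approximately 18. Section 11.11.3 selects the next dose by the highest probability of the target interval, among doses meeting the "overdose control constraint that there is less than 0.25 of probability for DLT rate > 0.33".

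**The concern.** A reader of 11.9 will expect the recommended dose to rest on no fewer than 18 evaluable subjects, because that section presents 18 as both guaranteed and necessary for accuracy. The rules that actually end escalation do not carry that guarantee. If rule (b) is met at 15 subjects, the sponsor either stops below the size that 11.9 calls necessary or keeps enrolling against 3.2.1.5. The practical stake is modest: a stated sample size and an accuracy claim that the operative rules do not support.

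**Working it through.** **The text alone.** The three rules are joined by OR, and the number 18 appears only in (a). That settles that fewer than 18 is possible. The rest measures how often.

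**Inputs.**
- Model (11.11.1): logit π(d) = log α + β log(d/800), with β > 0.
- Prior (11.11.2): (log α, log β) bivariate normal, means (−1.1493, −0.5514), SDs (2.0739, 1.5228), correlation −0.1943.
- Doses 200, 400, 600 and 800 mg (Table 3.1), overdose limit from 11.11.3, stopping rules from 3.2.1.5.

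**Reproducing the plan's figure.** At 800 mg, log(d/800) = 0, so the prior median is expit(−1.1493) = 24.1%. Numerical integration gives 8.0% at 200 mg. The plan says: "The median prior probabilities of DLT are set to be approximately 8% and 24.5% at 200 mg" and 800 mg respectively. The model is reproduced closely.

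**Assumed true rates.** The plan states none, so the prior medians are used. By 11.11.2 they are linear in log-dose on the logit scale:
- logit(0.08) = −2.442 and logit(0.245) = −1.126;
- slope = 1.317 / ln 4 = 0.950;
- 400 mg: −2.442 + 0.950 × 0.693 = −1.784, or 14.4%;
- 600 mg: −2.442 + 0.950 × 1.099 = −1.399, or 19.8%.

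**A rule (b) stop at 15, without dose skipping.** After 0/3 at 200 mg and 0/3 at 400 mg, the next cohorts go to 600 mg:

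| Data at 600 mg | P(target) at 600 | P(rate > 0.33) at 600 | P(rate > 0.33) at 800 | Next step |
|---|---|---|---|---|
| 1/3 | 0.318 | 0.115 | 0.264 | stay; 800 mg fails the limit |
| 2/6 | 0.445 | 0.163 | 0.363 | stay |
| 3/9 | 0.528 | 0.198 | 0.434 | rule (b) met, total 15 |

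The probability of exactly this sequence is 0.92³ × 0.856³ × [3 × 0.198 × 0.802²]³ = 0.779 × 0.628 × 0.382³ ≈ 0.027. No step requires a dose that the model excludes.

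**All paths.** Every outcome sequence in cohorts of 3 was enumerated with exact binomial weights. Skipping means the model may move up by more than one level.

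| Handling | No skipping | Skipping | Total at stop |
|---|---|---|---|
| Rule (b), on paths where some dose is always admissible | 3.8% | 9.9% | 15 |
| Rule (b), continuing at 200 mg whenever no dose is admissible | 9.0% | 14.0% | 12 or 15 |

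The early re-evaluation in 3.2.1.2 after 2 DLTs in the first 2 subjects moves the second row to 10.6% and 16.0%.

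**Sensitivity.** Other assumed true rates change the first row: 5/12/25/40% gives 5.9% and 7.9%, and 16/25/33/45% gives 4.6% and 3.4%. The plan says at least 3 per cohort; with cohorts of 4 to 6 and continuation at 200 mg, the share below 18 runs from 3% to 17%.

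**When no dose is admissible.** After 1 DLT in the first 3 at 200 mg, P(rate > 0.33) is 0.368, 0.486, 0.555 and 0.598 at 200, 400, 600 and 800 mg. All four exceed 0.25. At a true rate of 8%, at least one DLT in 3 has probability 1 − 0.92³ = 22.1%. What follows depends on a sponsor decision, so these trials are not part of the first row.

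**The case against.** The strongest reply is that the operative rules are explicit, are repeated in the synopsis, and sit beside a planned size of approximately 18. No subject's dose or protection depends on 11.9. A rule (b) stop also satisfies the plan's own 50% criterion, so ending at 15 is not a failure of precision by the plan's standard. All of this stands, and it limits the point to wording. It does not remove the conflict, because 11.9 says both that 18 will be treated and that 18 are needed.

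A second reply is that the percentages rest on inputs the plan does not fix: cohorts of exactly 3, and medians of a minimally informative prior used as true rates. That also stands. The figures show order of magnitude; the conflict itself needs none of them.

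A reader might go further and infer that about a third of trials end below 18. Stopping at once whenever no dose is admissible does give 31.9% without skipping and 33.8% with it. The documents do not support this as the consequence, for three reasons.

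- An immediate stop is not written anywhere. Section 3.2.1.2 lets the sponsor expand any cohort, consider lower doses, and weigh clinical data alongside the model; 3.2.1.4 gives enrollment and escalation decisions to safety review meetings. Expansion can restore admissibility: after 1/6 at 200 mg, P(rate > 0.33) is 0.120.
- Failing the limit is not treated as an automatic bar. Before any data the value at 200 mg is 0.256, already above 0.25, and the trial starts there.
- Of the 31.9% and 33.8%, 28.1 and 23.8 points are trials that end with no RDE, so they do not contradict a sentence about how many subjects support the RDE.

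A reader might also infer that the plan has no answer when every dose fails. Because β > 0, 200 mg is the least toxic of the four, so that event is the same as 200 mg exceeding the limit. Rule (c) is its natural home, although its threshold is undefined. This is missing detail within sponsor discretion and not a separate error.

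**Conclusion.** The point holds as a mismatch between 11.9 and 3.2.1.5. The guarantee of at least 18 is wrong as written, because rules (b) and (c) can end escalation earlier.

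Under cohorts of 3 and true rates at the prior medians, the share stopping at 15 under rule (b) is 3.8% without skipping and 9.9% with it. It rises to 9% to 14%, at 12 or 15 subjects, if the sponsor continues at 200 mg whenever no dose is admissible. Stops under rule (c), or straight after 1 DLT in the first 3 at 200 mg, would add to this, but they depend on a sponsor choice and yield no RDE. Nothing here shows that the dose rule is unsafe or that a rule (b) stop is inaccurate. Severity: minor.

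**What to change.** In 11.9, replace the guarantee with wording such as: *About 18 DLT-evaluable subjects are planned; fewer will be treated if escalation stops under 3.2.1.5(b) or (c).* This matches the synopsis. Drop the claim of an accurate estimate, or qualify it by reporting how often the rules stop early and how often they select a dose in the target interval.

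As an optional clarification, say in 3.2.1.5 whether rule (c) means that 200 mg exceeds the overdose limit of 11.11.3.

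The cost is wording only: no added subjects or procedures, and no change to the prior, the 0.25 limit or the stopping rules.
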